**Table 5 Study plan detailing the procedures during follow-up**

Visit Number	Follow-up Visit 1 a	Follow-up Visit 2 a	Details in Section
Study Week Procedure/Visit Window	8 weeks post last dose ±7D	12 weeks post last dose ±7D	
EQ-5D-5L, WPAI		X	5.3.1; 5.3.4
Complete physical examination, weight		X	5.2.2
Vital signs	X	X	5.2.3
Serum chemistry, haematology, and urinalysis	X	X	5.2.1
Urine pregnancy test in females of childbearing potential	X	X	5.2.1
PK blood sample	X	X	5.4.1
Immunogenicity blood sample d		X	5.4.3
TB questionnaire	X	X	5.2.6.3
SLEDAI-2K associated laboratory tests b	X	X	5.2.1
BILAG-2004 associated laboratory tests c	X	X	5.2.1
C-SSRS	X	X	5.2.5
BILAG-2004	X	X	5.1.4
CLASI	X	X	5.1.8
SLEDAI-2K	X	X	5.1.3
PGA	X	X	5.1.5
Joint count	X	X	5.1.9
Medical Resource Use Questionnaire	X	X	5.3.2
Assessment of AESIs	X	X	6.3; 6.6
Assessment of AEs/SAEs	X	X	6
Concomitant medications	X	X	7.7

AE = adverse event; AESI = Adverse Event of Special Interest; BILAG = British Isles Lupus Assessment Group; CLASI = Cutaneous Lupus Erythematosus; Disease Area and Severity Index; EQ-5D-5L = EuroQoL 5 dimensions; IFN = interferon; PD = pharmacodynamic; PGA = Physician's Global Assessment; PK = pharmacokinetic; SAE = serious adverse event; SLEDAI-2K = Systemic Lupus Erythematosus Disease Activity Index 2000; TB = tuberculosis; WPAI = Work Productivity and Activity Impairment; C-SSRS = Columbia Suicide Severity Rating Scale.

aFollow-up assessments are to be completed when participants complete the study (e.g., early termination or after the treatment period). Participants with early IMP discontinuation do not need to return for further safety follow-up assessments if they have been followed up for at least 12 weeks after the last dose during regularly scheduled clinical visits.

bSLEDAI-2K associated laboratory tests are C3, C4, CH50 complement, anti-ds DNA, urine protein/creatinine ratio. If central laboratory results are not available for SLEDAI-2K associated samples drawn on the date of visit, labs should be redrawn one time within 14 days of the SLEDAI assessment date.

cBILAG-2004 laboratory tests to include Coombs (if applicable), anticardiolipin, lupus anticoagulant, haptoglobin. Note: In order to avoid having to bring the participants back for a separate phlebotomy, the blood specimen for anticardiolipin, lupus anticoagulant, haptoglobin will be collected at the specified visits, however the blood will be stored at the central laboratory, and the analyses performed only if Investigator indicates that these tests need to be completed because of clinical suspicion of haemolytic anaemia or antiphospholipid

syndrome. Direct Coombs test samples will only be collected per Investigator's opinion at local laboratory and applicable BILAG assessment requirements for determining haemolytic anaemia.

dIn order to help understand the potential drug-relatedness of any hypersensitivity or anaphylaxis reaction, possible additional ADA testing (if not already scheduled for a visit) may be collected and analysed.

## **4.2 Enrolment/screening period**

At Screening, participants are assessed to ensure that they meet eligibility criteria. Once the participant signs the ICF, they are considered enrolled in the study. Participants who do not meet these criteria must not be randomised into the study.

Screening procedures will be performed according to the Screening Study Plan (Table 3), from Day -35 to Day -1. Once screening assessments needed to confirm eligibility and stratification are complete, all laboratory results are reported, and central review is complete, a participant may be randomised. There does not need to be 35 days between screening and Randomisation (Day 1).

Chest radiograph and Cervical Cancer Screening Test may be completed anytime during the screening period as long as all results have been reviewed by Investigator prior to randomisation.

If a participant does not meet eligibility criteria on the basis of a laboratory value then the laboratory value may be repeated once within the screening period.

### **4.2.1 Other considerations for screening**

#### **4.2.1.1 Oral examination**

In several biological programs there have been serious infections and/or death related to Ludwig's angina. Although this has not been seen in the anifrolumab program, Investigators should check a participant's oral cavity and review their dental health carefully during the screening process. While a dental examination is not required prior to enrolment in this study, Investigators are cautioned to consider carefully whether participants have active caries or a dental infection that might impact on participant safety prior to enrolment.

#### **4.2.1.2 Mammography**

As participants with SLE have impaired immune response, are treated with immunosuppressants and are at potential risk for malignancy, it is recommended that participants enrolled into the study are compliant and up to date with local recommendations for mammography or other screening procedures for breast cancer.

#### **4.2.2 Re-screening participants who screen fail**

If a participant fails screening for inadequate disease activity, or other reason, which, in the opinion of Investigator, may change to make the participant eligible, the participant may be re-screened **1 time**. The same E-code that the participant received at the first enrolment will be used. In this case, the participant will re-sign the informed consent document. If the participant fails screening twice, they may not undergo further screening for this study. Initial screening procedures completed within the 35 days prior to participant randomisation need not be repeated during the re-screen visit.

#### **4.3 Treatment period**

Procedures during the Treatment Period will be performed according to the Treatment Period Study Plan (Table 4), from Randomisation (Week 0) to Week 52. The participant-reported outcome assessments should be completed by the participant (unassisted by spouse, family members or friends) prior to all other evaluations, and prior to the infusion, as disease assessments/clinical evaluations may confound the results.

Before scheduling the Randomisation (Day 1) visit, ensure notification from the DACRT has been received, confirming that participant meets disease activity eligibility (Inclusion Criterion No. 9, 10 and 11). The DACRT will review all data necessary to characterize participant SLE in relation to the SLEDAI-2K, BILAG-2004, and PGA assessments (including central laboratory results).

On Day 1, ensure participant meets eligibility criteria, including Day 1 assessments according to the Treatment Period Study Plan (Table 4). Participants confirmed to be eligible will be randomised. Investigational medicinal product (anifrolumab or placebo) should be administered the same day the investigational medicinal product kit number is assigned and the same day all randomisation study procedures are performed.

Participants will have scheduled visits at 4-week ( $\pm 7$  days) intervals to complete protocol-specified assessments and investigational medicinal product administration according to the Treatment Period Study Plan (Table 4). From Week 4 through Week 48, Investigational medicinal product (anifrolumab or placebo) administration and required study procedures are preferred to be completed in the same day, but are also allowed to be completed within 24 hours if needed.

The last dose of investigational medicinal product will be administered on Week 48. At Week 52, participants will have an End of Treatment (EOT) visit. For participants who prematurely discontinue investigational medicinal product and are not willing to continue to participate in the study refer to Section 3.9 and Section 4.3.1.

#### **4.3.1 Follow up visits after premature discontinuation of investigational medicinal product**

**Participants who discontinue investigational medicinal product (see Section 3.9) will be asked to return for all regularly scheduled clinic visits.** If the participant is unwilling to complete all regularly scheduled clinic visits, the participant should complete the EDV within 4 weeks of the last dose of investigational medicinal product, as well as Follow-up Visit 1 and Follow-up Visit 2 (8 and 12 weeks after the last dose) unless consent is withdrawn.

If the participant is unwilling to continue with any study visits, including EDV visit, at a minimum, the following assessments should be completed:

- SLEDAI-2K and the associated laboratory tests (anti-dsDNA antibodies, C3, C4, CH50).
- BILAG-2004 laboratory tests to include anticardiolipin, lupus anticoagulant, haptoglobin and Coombs (Coombs will be performed at local laboratory as applicable per BILAG assessment requirements).
- Note: In order to avoid having to bring the participant back for a separate phlebotomy, the anticardiolipin, lupus anticoagulant, and haptoglobin blood specimen will be collected at all specified visits, however the blood will be stored at the central laboratory, and the analyses performed only if Investigator indicates that these tests need to be completed because of clinical suspicion of haemolytic anaemia or antiphospholipid syndrome. Direct Coombs test samples will only be collected per Investigator's opinion at local laboratory and applicable BILAG assessment requirements for determining haemolytic anaemia.
- CLASI
- PGA
- Joint count

The following safety assessments will also be completed:

- Serum chemistry, haematology, urinalysis
- Urine for protein, creatinine and urine-protein-creatinine ratio
- Lipid Profile defined in Section 5.2.1.1
- Immunology Profile defined in Section 5.2.1.1
- Vital signs
- Complete physical examination, weight
- AE including AESIs
- Cardiovascular risk assessment

- TB questionnaire
- Concomitant medications

If the participant does not agree to do this, they will be asked if they can be followed on a monthly basis via telephone calls until 12 weeks post the last dose of IMP. At these calls, they will be asked about AEs/SAEs, lupus symptoms, and lupus medications. Steroid bursts will also be captured.

Adverse events will be followed up per Section 6.4.2.

#### **4.3.2 Lost to follow-up**

A participant will be considered lost to follow-up if he or she repeatedly fails to return for scheduled visits and is unable to be contacted by the study site.

The following actions must be taken if a participant fails to return to the clinic for a required study visit:

- The site must attempt to contact the participant and reschedule the missed visit as soon as possible and counsel the participant on the importance of maintaining the assigned visit schedule and ascertain whether or not the participant wishes to and/or should continue in the study.
- Before a participant is deemed lost to follow-up, Investigator or designee must make every effort to regain contact with the participant (where possible, 3 telephone calls and, if necessary, a certified letter to the participant's last known mailing address or local equivalent methods). These contact attempts should be documented in the participant's medical record.
- Should the participant continue to be unreachable, he/she will be considered to have withdrawn from the study.

#### **4.4 Unscheduled visit**

There may be times a participant needs to have an unscheduled visit. Investigator should determine the assessments to be completed based on the reason for the unscheduled visit and for participant safety. Concomitant medications and AEs should be completed whenever a participant has an unscheduled visit.

If a participant presents for an unscheduled visit in lieu of a regularly scheduled visit (i.e., the participant is seen for safety and efficacy assessments when a regularly scheduled dosing or follow-up visit is missed), Investigator should complete all possible safety and efficacy assessments applicable to the missed visit. Unscheduled efficacy assessments should not be collected in between completed regular study visits.

## 4.5 Follow-up period

Procedures will be performed according to the Follow-up Period Study Plan ([Table 5](#)).

Participants who complete the double-blind treatment period will have follow-up visits at Week 56 and Week 60. Participants who are withdrawn from the investigational medicinal product and do not agree to complete the 52-week study period, should complete the EDV visit within 4 weeks of the last dose of IMP, and be followed 8 and 12 weeks after the last dose by completing the Follow-up Visit 1 and 2 assessments (see [Section 3.9](#)).

## 4.6 Study completion and end of study

An individual participant will be considered to have completed the study if the participant was followed up until the end of the study (Week 60, or Week 52 for those participants who prematurely discontinue the investigational medicinal product and complete a minimum of 12 weeks of follow-up) regardless of the number of doses of investigational medicinal product that were received. The end of the study (“study completion”) is defined as the date of the last protocol specified visit/assessment for the last participant in the study.

## 5 STUDY ASSESSMENTS

The Web Based Data Capture (WBDC) system will be used for data collection and query handling. Investigator will ensure that data are recorded on the eCRF as specified in the study protocol and in accordance with the instructions provided.

Investigator ensures the accuracy, completeness, and timeliness of the data recorded and of the provision of answers to data queries according to the Clinical Study Agreement (CSA). Investigator will sign the completed eCRF. A copy of the completed eCRF will be archived at the study site.

### 5.1 Efficacy assessments

Efficacy measurements will be made at the times indicated in the Study Plan (see [Table 3](#) for assessments to be performed at Screening, [Table 4](#) for Treatment Period, and [Table 5](#) for Follow-up). Participant-reported outcome assessments should be completed by the participant, unassisted by spouse, family members or friends.

#### 5.1.1 Training and certification for Systemic Lupus Erythematosus assessments

In order to maintain consistent evaluation of SLE disease activity across study sites, training and certification of Investigators and designated site personnel who will be completing the disease evaluations listed below will be conducted.

- SLEDAI-2K
- BILAG-2004
- PGA
- SDI
- CLASI
- Swollen and tender joint count evaluation

The SLEDAI-2K, BILAG-2004, PGA, and CLASI must be administered by Investigator or another qualified physician, unless prior sponsor approval has been obtained for any other clinically trained site personnel with documentation of adequate assessment experience per the study central review plan. The joint count evaluation can be completed by other site personnel who, as per Investigator discretion, are qualified to perform the assessments and have at least one year of experience administering the joint count evaluation. Training will include printed training materials, digital media and formal presentations, as well as web-based training modules.

After attending study presentations (i.e., Investigator Meeting) or after completion of online training modules, all Investigators and designated site physicians must pass an online

examination in order to obtain certification for all disease evaluation assessments, with the exception of the joint count evaluation. Investigators and designated site personnel must be trained and certified prior to participants entering screening at their respective sites. All assessments and certifications must be renewed via the study online training website prior to expiration and must remain current (not expire) throughout the course of the study. If there is a change in site personnel over the course of the study, new Investigators or physicians must be certified prior to performing the SLEDAI-2K, BILAG-2004, PGA, and CLASI assessments.

It is expected that Investigator will ensure all joint count assessors have adequate experience (minimum of 1 year) and training qualifications to perform the swollen and tender joint count assessment. Assessors (including any new Investigators or site personnel) must complete the online joint count training module and obtain certification prior to performing any joint assessment.

Documentation of all training will be maintained in the site's study file.

Over the course of the study, Investigator assessments for a given participant should be completed by the same trained and/or certified Investigator, designated physician, or qualified site personnel (as described above) whenever possible.

#### **5.1.2 Disease activity central review team**

The study has a DACRT made up of individuals who are medically-qualified individuals and/or support staff who assist in the ongoing management of this trial. The DACRT will review all data necessary to characterize participant SLE; however, the group will remain blinded for the duration of the study. DACRT Group members will have access to an independent expert on SLE disease activity indices for unanticipated issues with regards to interpretation of these indices.

The DACRT will be utilized to confirm eligibility during screening and will be utilized throughout the study to confirm SLEDAI-2K, BILAG-2004, and PGA scoring. The DACRT will also ensure that the completion of efficacy assessments by Investigators is of proper quality and consistency.

If there is inconsistency between assessments, additional clarification and training on these assessments will be provided through the DACRT.

#### **5.1.3 Systemic Lupus Erythematosus Disease Activity Index 2000**

The SLEDAI-2K index (see [Appendix E](#)) consists of a list of organ manifestations, each with a definition. A certified Investigator or designated physician will complete the SLEDAI-2K assessment and decide whether each manifestation is "present" or "absent" in the last 4 weeks.

The assessment also includes the collection of blood and urine for assessment of the laboratory categories of the SLEDAI-2K.

The SLEDAI-2K assessment consists of 24 lupus-related items. It is a weighted instrument, in which descriptors are multiplied by a particular organ's "weight". For example, renal descriptors are multiplied by 4 and central nervous descriptors by 8 and these weighted organ manifestations are totalled into the final score. The SLEDAI-2K score range is 0 to 105 points with 0 indicating inactive disease. The SLEDAI-2K scores are valid, reliable, and sensitive clinical assessments of lupus disease activity. The SLEDAI-2K calculated using a timeframe of 30 days prior to a visit for clinical and laboratory values has been shown to be similar to the SLEDAI-2K with a 10-day window (Touma et al, 2010). A timeframe of 28 days will be used in this study.

The "Clinical" SLEDAI-2K score is the SLEDAI-2K assessment score without the inclusion of points attributable to any urine or laboratory results including immunologic measures. Its use may permit earlier clinical decisions to be made without waiting for immunologic measures (including anti-dsDNA antibodies and C3, C4, and CH50 complement levels). However, in any circumstance where the "Clinical" SLEDAI-2K score is used, sites must subsequently update the SLEDAI-2K assessment when laboratory data become available so that the full SLEDAI-2K score is made available to the Sponsor.

A quick Reference Guide will be provided to all study personnel, which contains detailed protocol-specific clarifications and extensions of SLEDAI-2K clinical parameter definitions and a guidance for correlating SLEDAI-2K and BILAG-2004 clinical parameters.

#### **5.1.4 British Isles Lupus Assessment Group 2004**

The BILAG-2004 is a translational index with 9 organ systems (General, Mucocutaneous, Neuropsychiatric, Musculoskeletal, Cardiorespiratory, Gastrointestinal, Ophthalmic, Renal and Haematology) that is able to capture changing severity of clinical manifestations (see [Appendix F](#)). It has ordinal scales by design and does not have a global score; rather it records disease activity across the different organ systems at a glance by comparing the immediate past 4 weeks to the 4 weeks preceding them. It is based on the principle of physicians' Intention-to-Treat and categorizes disease activity into 5 different levels from A to E:

- Grade A represents very active disease requiring immunosuppressive drugs and/or a prednisone dose of > 20 mg/day or equivalent
- Grade B represents moderate disease activity requiring a lower dose of corticosteroids, topical steroids, topical immunosuppressives, antimalarials, or NSAIDs
- Grade C indicates mild stable disease
- Grade D implies no disease activity, but the system has previously been affected

- Grade E indicates no current or previous disease activity

Although the BILAG-2004 was developed based on the principle of Intention-to-Treat, the treatment has no bearing on the scoring index. Only the presence of active manifestations influences the scoring.

#### **5.1.4.1 Protocol-specific clarification and extension of BILAG-2004 definitions**

A quick Reference Guide will be provided to all study personnel, which contains detailed protocol-specific clarifications and extensions of BILAG-2004 clinical parameter definitions and guidance for correlating SLEDAI 2K and BILAG-2004 clinical parameters. Please refer to this guide when completing disease activity assessments. Important extensions of selected BILAG-2004 glossary definitions are included as follows:

Protocol-specific extensions of BILAG-2004 and SLEDAI-2K clinical parameter definitions:

- (a) BILAG-2004 A or B score in the musculoskeletal organ system due to active polyarthritis, defined as follows:
  - “BILAG 2004 A”: severe arthritis (BILAG 2004 #41) manifested by observed active synovitis in  $\geq 2$  joints with marked loss of functional range of movements and significant impairment of basic activities of daily living (ADL), that has been present on several days cumulatively over the past 4 weeks, including at the time of the Screening visit. Basic ADLs are defined as the following activities which require assistance or assistive devices (at least 1 must be present and documented in source): ambulation, toileting, grooming including bathing, dressing, feeding oneself.
  - For scoring BILAG-2004 as severe arthritis (A), the affected joints must have clear signs of synovitis (tender AND swollen) that is due to SLE activity with significant impact on basic daily activities and need for assistance as above and non-SLE related causes that may affect joint activity and basic ADLs such as osteoarthritis or obesity must be ruled out. The joint activity would require treatment with high dose systemic steroids and/or immunomodulators/immunosuppressives including biologics. Although activity in only 2 joints could qualify for a BILAG A score for arthritis, this is expected to occur very rarely.
  - BILAG 2004 B”: moderate arthritis or tendonitis or tenosynovitis (BILAG 2004 #42) defined as tendonitis/tenosynovitis or active synovitis in  $\geq 1$  joint (observed or through history) with some loss of functional range of movements which leads to some loss of functional range of motion as manifested by effects on instrumental ADLs (such as cooking, driving, using the telephone or computer, shopping, cleaning, etc), which has been present on several days over the last 4 weeks and is present at the time of the Screening visit. The joint activity must be due to SLE with other causes excluded and with activity that would need treatment with

moderate systemic steroid doses, intraarticular steroid injection and/or antimalarials. Although activity in only 1 joint could qualify for a BILAG B score for arthritis, this is expected to occur very rarely

- (b) BILAG-2004 and SLEDAI-2K “lupus headache”: lupus headache is rare, migraine, tension or cluster headaches should not be recorded. Lupus headache should only be recorded if it is disabling, lasts at least 3 days, and does not respond to narcotics. It is expected that its severity would prompt formal testing (lumbar puncture, magnetic resonance imaging [MRI], CT, etc) and require corticosteroids and/or immunosuppressants and potentially hospitalisation for treatment. Lupus headache is considered a manifestation of lupus cerebritis.

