#### 6.4.9 Disease progression

Disease progression can be considered as a worsening of a participant's condition attributable to SLE. It may be an increase in the activity or severity of the existing manifestations of SLE or the appearance of new manifestations. **Worsening of SLE should not be reported as an AE, unless the signs and symptoms meet criteria for an SAE or lead to discontinuation of the investigational medicinal product.** New manifestation or worsening of existing manifestations of SLE should be reported as "new" or "worsening" in the BILAG-2004, and recorded in the SLEDAI-2K, as appropriate.

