## Appendix F British Isles Lupus Assessment Group-2004

These are for information purposes and representation only and serve as an example to be used in the study.

**BILAG-2004 INDEX** Centre: \_\_\_\_\_ Date: \_\_\_\_\_ Initials/Hosp No: \_\_\_\_\_

◆ Only record manifestations/items due to SLE Disease Activity

◆ Assessment refers to manifestations occurring in the last 4 weeks (compared with the previous 4 weeks)

◆ TO BE USED WITH THE GLOSSARY

Record: ND Not Done

0 Not present

1 Improving

2 Same

3 Worse

4 New

Yes/No OR Value (where indicated)

\*Y/N Confirm this is due to SLE activity (Yes/No)

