Scores for the SLEDAI organ systems will be derived in the way as SLEDAI-2K but using the scores for the respective items only.

BILAG-2004

The BILAG-2004 contains 97 (from Appendix F of CSP) clinical and laboratory parameters which are divided into a translational index with 9 organ systems (Constitutional, Mucocutaneous, Neuropsychiatric, Musculoskeletal, Cardiorespiratory, Gastrointestinal, Ophthalmic, Renal and Hematology). The first 7 organ systems (Constitutional, Mucocutaneous, Neuropsychiatric, Musculoskeletal, Cardiorespiratory, Gastrointestinal, Ophthalmic) contain clinical parameters which are assessed by the treating physician as new (4), worse (3), same (2), improving (1) and not present (0). The Renal and Hematologic scoring is based on laboratory values. BILAG organ system scores are assigned into 5 different levels as A, B, C, D or E scores to all study visits by strictly following this Index Scoring. Results from the original scores are used for calculation of the primary efficacy endpoint, BICLA response at Week 52, defined in Section 4.2.1.1. The treatment has no bearing on the scoring index. Only the presence of active manifestations influences the BILAG-2004 scoring.

BILAG-2004 grades will be presented by organ system. Furthermore, a BILAG-2004 global score is derived by summing-up the numerical score equivalents for each organ system with the numerical score equivalents given as: A = 12, B = 8, C = 1, D = 0, and E = 0.

Unless otherwise defined, scores that are derived from summing up items will be considered missing if any of the items are still missing after applying the LOCF (last observation carried forward) rules. This should apply to both SLEDAI-2K and BILAG-2004.

Physician's Global Assessment (PGA)

The PGA is a modification of the classic analogue scale in that it is anchored with numbers from 0 to 3 demarcating no, mild, moderate, and severe disease. The number 3 indicates severe disease and is at the end of the scale. Any disease rated greater than 2.5 is very severe. The range of moderate disease covers approximately 1.5 to 2.4. Mild disease falls below 1.5. The instrument is similar to a logarithmic scale, with greater distances or demarcations possible among more mild-moderate symptoms. This is a global assessment, factoring in all aspects of the participant's lupus disease activity. It should not reflect non-lupus medical conditions.

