4.2.4 Key Secondary Endpoint - Flares

4.2.4.1 Definition

The key secondary endpoint used to evaluate the effect of anifrolumab versus placebo on flares is the difference in annualized flare rate through Week 52.

A flare is defined as either 1 or more new BILAG-2004 A or 2 or more new BILAG-2004 B items compared to the previous visit (i.e., a worsening from an E, D, or C score to a B score in at least 2 organ systems or a worsening from an E, D, C, or B score to an A score in any one organ system compared to the previous visit).

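### Protocol Section 5.1.4.1 ties BILAG-2004 arthritis grades A and B to the Screening visit, so read literally arthritis that first arises later cannot count toward a BILAG flare through items 41/42

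*Protocol*

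**What the plan says.** Protocol Section 5.1.4.1 gives study-specific definitions for a musculoskeletal A or B due to active polyarthritis. Grade A (item 41, severe arthritis) needs synovitis "that has been present on several days cumulatively over the past 4 weeks, including at the time of the Screening visit". Grade B (item 42, moderate arthritis, tendonitis or tenosynovitis) needs activity "which has been present on several days over the last 4 weeks and is present at the time of the Screening visit". The section offers no other wording for later visits and does not confine these definitions to eligibility.

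Elsewhere BILAG-2004 is a rolling assessment:
- Protocol Section 5.1.4 describes it as "comparing the immediate past 4 weeks to the 4 weeks preceding them".
- The form in Appendix F uses the same window and has a separate code for a new manifestation.
- Protocol Section 6.4.9: "New manifestation or worsening of existing manifestations of SLE should be reported as" new or worsening, as the case may be, in BILAG-2004.
- SAP Section 4.1.6.1 assigns A to E "scores to all study visits by strictly following this Index Scoring".
- Protocol Tables 4 and 5 schedule BILAG-2004 at every treatment and follow-up visit.

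On the endpoint, SAP Section 4.2.4.1 states: "A flare is defined as either 1 or more new BILAG-2004 A or 2 or more new BILAG-2004 B items compared to the previous visit". A new A or two new Bs is also the BILAG worsening criterion of BICLA (Protocol Section 8.4.1) and of SRI(4) (Protocol Section 8.4.2.1).

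**The concern.** A condition that suits an eligibility assessment has been written into a general scoring definition. At Screening it does what is wanted. At any later visit it asks about the wrong date: whether arthritis was there at Screening, not whether it was active in the weeks before the visit being scored.

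The flare endpoint is the most exposed, because it has no component other than new BILAG grades. Time to first flare (SAP Section 4.2.4.7) uses the same definition. If sites follow the text, flares made up wholly or partly of new arthritis are lost, precision falls, and sites that read the phrase differently score like patients differently. If the loss is proportional in both arms, the flare rate ratio may move little. If arthritis makes up a different share of flares in the two arms, the ratio can shift.

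**Working it through.** There is no stated figure to reproduce. The check compares the definitions with the visit schedule, then traces each route by which new arthritis could count.

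**1. Can the grade A condition be met after Screening?** Taken strictly, the Screening visit must lie inside the past 4 weeks (28 days). Inputs: Screening runs from Day -35 to Day -1 (Protocol Section 4.2), visits have a window of ±7 days (Table 4), Week 4 is Day 29 and Week 8 is Day 57 (SAP Section 3.3.2), and there is no Day 0 (SAP Section 3.3).
- Day 1: the Screening visit can be 35 days back. 35 - 28 = 7 days outside the window, so the condition can fail even at baseline.
- Week 4 on schedule, latest possible Screening (Day -1): 29 - 1 + 1 = 29 days, which exceeds 28. Only an early visit after a short Screening can qualify (Day 22 gives 22 days).
- Week 8 at its earliest (Day 57 - 7 = Day 50): 50 - 1 + 1 = 50 days. The condition fails from here on, even for arthritis that has persisted since Screening.

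On a looser reading (active in the past 4 weeks and also present at Screening), persisting or recurrent arthritis qualifies, but arthritis first arising after Screening never does. Grade B says this directly.

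**2. Arthritis first arising after Day 1, by endpoint.**
- Flare: the only route is a new A, or new Bs in at least two organ systems, against the previous visit. Items 41/42 are closed, so the arthritis contributes nothing.
- BICLA: the BILAG criterion is closed for items 41/42. SLEDAI-2K has no Screening condition (Appendix E) and gives arthritis 4 points. Any net rise above 0 fails BICLA, so the participant passes that criterion only if other items have fallen by at least 4 (4 - 4 = 0). A PGA rise of 0.30 or more also fails it.
- SRI(4): the BILAG criterion is likewise closed. The same 4 points mean other items must fall by at least 8 to reach the required reduction (4 - 8 = -4).

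The SLEDAI-2K route is not a complete substitute. Its arthritis item needs at least 2 joints, while grade B can rest on 1 joint or on tenosynovitis. The protocol expects a single-joint B to be very rare.

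**3. Arthritis arising between Screening and Day 1.** Baseline is Day 1 (Protocol Section 8.4). Under the literal text this arthritis is not a baseline A or B, so the BICLA requirement that every baseline A and B improve does not reach it.

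**4. Arthritis present at Screening that improves and recurs.** It meets the grade B wording and can be a new B against the previous visit. This case is not lost.

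**5. Is the definition meant for Screening only?** The protocol labels such rules elsewhere: inclusion criteria 9(b) and 10 both say they apply at screening. The companion definition in Section 5.1.4.1, lupus headache, has no Screening condition. Nothing in the section marks the arthritis definitions as eligibility-only.

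**The case against.** The best reply is that this is leftover eligibility wording that no trained assessor would apply literally. The strict grade A reading defeats itself within weeks. Sections 5.1.4 and 6.4.9, Appendix F and the SAP all show how new manifestations are to be scored. Assessors are trained and certified (Section 5.1.1), and the central review team confirms BILAG scoring throughout (Section 5.1.2). The instruction "Please refer to this guide when completing disease activity assessments" points to a separate Quick Reference Guide, not to Section 5.1.4.1, and that guide may carry correct wording.

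Much of this stands. It makes misreading less likely and means that actual practice cannot be judged from these documents. It does not remove the conflict in the text. Nor is central review shown to repair it: the modified-scoring task in Section 5.1.4.2 is to find false A and B grades, not to restore grades that were never given.

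A reader might infer three stronger things that the documents do not support:
- That no new arthritis can be scored as worsening at all. It still counts in BICLA and SRI(4) through SLEDAI-2K and the PGA.
- That a participant without arthritis at Screening can never have a musculoskeletal A or B. The condition covers items 41/42 only; myositis (items 39 and 40) is untouched.
- That a share of lost flares can be stated. The documents give neither the proportion of participants without qualifying arthritis at Screening nor the share of new grades that arthritis supplies.

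**Conclusion.** The definitions as written give the wrong result after Screening and contradict the protocol's own rolling window. Arthritis first arising after Screening cannot receive an A or B through items 41/42, and so cannot count toward a flare or the BILAG worsening criterion of BICLA and SRI(4). The gap has no substitute route for flares and a partial one for BICLA and SRI(4).

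No numerical size can be given. The conclusion rests on reading the text literally. It does not show that any visit was mis-scored, because the Quick Reference Guide and the modified-BILAG charter are not available. It should be corrected, since the wording governs a key secondary endpoint and a component of the primary one.

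**What to change.** In Protocol Section 5.1.4.1, limit the Screening-visit condition expressly to eligibility scoring under inclusion criterion 10. State that at all later visits items 41/42 are graded over the 4 weeks before the visit being scored, in line with Sections 5.1.4 and 6.4.9 and Appendix F. Do not simply swap in presence on the day of the visit: that would drop arthritis active within the window but resolved by then, and would conflict with Appendix F and with grade B, which accepts history as well as observation.

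Align the Quick Reference Guide and send sites a clarification. Before the primary database lock, have the existing blinded central review confirm that post-baseline items 41/42 were scored this way. State how a corrected grade reaches each endpoint, because SAP Section 4.1.6.1 uses original BILAG scores for BICLA while Protocol Section 8.4 uses adjudicated values where applicable.

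Cost: two phrases, one site letter, and a check with an upper limit of 260 x 13 = 3,380 post-baseline assessments to Week 52. Joint counts are taken at the same visits, so the check can be narrowed to visits with tender and swollen joints but no grade through items 41/42.
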